11.3 Safety pause and prompt PSRT AE review

When a trial is placed on safety pause, all infusions with the product related to the event that triggered the pause will be held until further notice. The AEs that will lead to a safety pause or prompt HVTN 116 PSRT AE review are summarized in [Table 11-1](#). Infusions may be suspended for safety concerns other than those described in the table, or before pause rules are met, if, in the judgment of the HVTN 116 PSRT, participant safety may be threatened. Criteria for an individual participant's departure from the infusion schedule are listed in [Section 7.3](#).

Table 11-1 AE notification and safety pause/AE review rules

Event and relationship to study products	Severity	HVTN CRS action ^a	HVTN Core action
SAE, related	Grade 5 or Grade 4	Phone immediately, email and submit forms immediately	Immediate pause
SAE, not related	Grade 5	Phone immediately, email and submit forms immediately	Immediate HVTN 116 PSRT notification
SAE, related	Grade 3	Email and submit forms immediately	Prompt HVTN 116 PSRT AE review to consider pause
AE ^b , related	Grade 4 or 3	Email and submit forms immediately	Prompt HVTN 116 PSRT AE review to consider pause

^a Phone numbers and email addresses are found on the Protocol home page on the HVTN Members' site (<https://members.hvtn.org/protocols/hvtn116>).

^b Does not include subjective reactogenicity symptoms (infusion site pain, tenderness, fatigue/malaise, myalgia, arthralgia, chills, headache, and nausea). Does include pruritus, which should be reviewed promptly.

For all safety pauses, HVTN Core notifies the HVTN 116 PSRT, HVTN Regulatory Affairs, DAIDS Pharmaceutical Affairs Branch (PAB), DAIDS Regulatory Affairs Branch (RAB), DAIDS Safety and Pharmacovigilance Team (SPT), and participating HVTN CRSs. When an immediate safety pause is triggered, HVTN Core notifies the SMB.

Once a trial is paused, the HVTN 116 PSRT reviews safety data and decides whether the pause can be lifted or permanent discontinuation of infusions is appropriate, consulting the SMB if necessary. HVTN Core notifies the participating HVTN CRSs, HVTN Regulatory Affairs, DAIDS PAB, DAIDS RAB, and DAIDS SPT of the decision regarding resumption or discontinuation of study infusions. Based on the HVTN 116 PSRT assessment, DAIDS RAB notifies the FDA as needed.

If an immediate HVTN 116 PSRT notification or prompt HVTN 116 PSRT AE review is triggered, HVTN Core notifies the HVTN 116 PSRT as soon as possible during working hours (US Pacific Time)—or, if the information was received during off hours, by the morning of the next work day. If a prompt HVTN 116 PSRT AE review cannot be completed within 72 hours of notification (excluding weekends and US federal holidays), an automatic safety pause occurs.

The HVTN requires that each CRS submit to its IRB/EC and any applicable RE protocol-related safety information (such as IND safety reports, notification of infusion holds due to the pause rules, and notification of other unplanned safety pauses). CRSs must also follow all applicable RE reporting requirements.

In addition, all other AEs are reviewed routinely by the HVTN 116 PSRT (Section 11.4.2).

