7.3.3 Discontinuing study product administrations for a participant

Under certain circumstances, an individual participant's infusions will be permanently or temporarily discontinued. Specific events that will result in stopping a participant's infusion schedule include:

- Co-enrollment in a study with an investigational research agent (rare exceptions allowing for the continuation of infusions may be granted with the unanimous consent of the HVTN 116 PSRT).
- Clinically significant condition (ie, a condition that affects the immune system or for which continued infusions and/or blood draws may pose additional risk), including but not limited to the following:
 - Pregnancy (infusions will be stopped while a participant is pregnant. If the participant is no longer pregnant and can be infused within an appropriate visit window, infusions may resume, see Section [7.3.1](#));
 - HIV infection;
 - Any grade 4 local or systemic reactogenicity symptom, lab abnormality, or AE that is subsequently considered to be related to study product administration;

- Any grade 3 lab abnormality or other clinical AE (exception: fever or vomiting and subjective local and systemic symptoms) that is subsequently considered to be related to study product administration; or
- Clinically significant type 1 hypersensitivity reaction associated with study product administration. Consultation with the HVTN 116 PSRT is required prior to subsequent infusions following any type 1 hypersensitivity reaction associated with study product administration; or
- Investigator determination in consultation with Protocol Team leadership (eg, for repeated nonadherence to study staff instructions).

Participants discontinuing study product for reasons other than HIV infection should be counseled on the importance of continuing with the study and strongly encouraged to participate in follow-up visits and protocol-related procedures per the protocol for the remainder of the trial, unless medically contraindicated.

Participants diagnosed with HIV infection during the study should be encouraged to participate in follow-up visits as indicated in Section 9.14.

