9.10.1 Assessment of systemic and local symptoms

Systemic symptoms include increased body temperature, malaise and/or fatigue, myalgia, headache, chills, arthralgia, nausea, pruritus, diarrhea, and vomiting. Local symptoms include pain and/or tenderness proximal to the infusion site. The daily maximum severity reached for each symptom during the assessment period is reported.

Body temperature is measured by oral or infrared thermometry and reported in degrees Celsius. If temperature is measured in Fahrenheit, the conversion to Celsius should be documented in the participant's chart note. A measurement is taken once daily during the assessment period and should be repeated if participant is feeling feverish.

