11.4.2 Weekly review

During the infusion phase of the trial, the HVTN 116 PSRT reviews clinical safety reports on a weekly basis and conducts calls to review the data as appropriate. After the infusions and the following two-week safety visit are completed, less frequent reporting and safety reviews may be conducted at the discretion of the HVTN 116 PSRT. HVTN Core reviews reports of clinical and laboratory AEs. Events identified during the review that are considered questionable, inconsistent, or unexplained are referred to the HVTN CRS clinic coordinator for verification.

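### Footnote b of Table 11-1 exempts subjective infusion symptoms from prompt PSRT review at Grade 4 as well as Grade 3, a small escalation gap beside the Grade 4 stopping rule in 7.3.3

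*Protocol*

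**What the plan says.** **Trial-level rule (Protocol 11.3, Table 11-1).** One row covers related AEs of Grade 4 or 3. The site must email and submit forms immediately, and HVTN Core starts a prompt PSRT review to consider a pause. Footnote b sits on that row: "Does not include subjective reactogenicity symptoms (infusion site pain, tenderness, fatigue/malaise, myalgia, arthralgia, chills, headache, and nausea". It then puts pruritus back under prompt review. It says nothing about grade.

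Prompt review carries a deadline: "If a prompt HVTN 116 PSRT AE review cannot be completed within 72 hours of notification", not counting weekends and US federal holidays, infusions pause automatically.

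**Individual rule (Protocol 7.3.3).** The grades are handled in separate bullets. The first stops infusions for "Any grade 4 local or systemic reactogenicity symptom, lab abnormality, or AE that is subsequently considered to be related" to the product, with no carve-out. The second stops them for "Any grade 3 lab abnormality or other clinical AE (exception: fever or vomiting and subjective local and systemic symptoms") when related. The subjective exemption appears only in the second, Grade 3, bullet.

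**Symptoms collected (Protocol 9.10.1).** "Systemic symptoms include increased body temperature, malaise and/or fatigue, myalgia, headache, chills, arthralgia, nausea, pruritus, diarrhea, and vomiting". Pain and/or tenderness are the local symptoms.

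**Other routes.** "Infusions may be suspended for safety concerns other than those described in the table, or before pause rules are met", if the PSRT judges that safety may be threatened. Section 11.3 adds that "all other AEs are reviewed routinely by the HVTN 116 PSRT", and 11.4.2 says that in the infusion phase "the HVTN 116 PSRT reviews clinical safety reports on a weekly basis".

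**The concern.** For related, non-serious subjective symptoms the two rules agree at Grade 3: the participant is not stopped and no prompt review follows. At Grade 4 they part. The protocol regards the symptom as severe enough to withhold product from the person who had it, yet sets no deadline for asking whether others should go on receiving the same product.

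The exempted terms are central to infusion safety. Section 4.8 lists chills, nausea and headache among the usual side effects of monoclonal antibodies and says that most infusion-related events occur within 24 hours of starting the infusion.

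At stake is timing, not capture. The data would still be collected, tabulated and seen by the PSRT. What is missing is the site's immediate notice under Table 11-1, a fixed time for the PSRT to act, and the automatic pause that enforces it.

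**Working it through.** The plan gives no figure for this point, so the check is mainly a comparison of rules.

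**Step 1: what footnote b removes.** It names eight terms. Six are among the ten solicited systemic symptoms in 9.10.1: fatigue/malaise, myalgia, arthralgia, chills, headache and nausea. The other two, pain and tenderness, are the local symptoms. Raised temperature, vomiting, diarrhea and pruritus stay in the row.

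**Step 2: the rules side by side, for related events.**

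| Event | 7.3.3 (participant) | Table 11-1 (trial) |
|---|---|---|
| Grade 3 subjective symptom, non-serious, in the reactogenicity window | Not stopped | Exempt; routine review |
| Grade 4 subjective symptom, non-serious, in the window | Stopped | Exempt; routine review |
| Grade 4 symptom of the same kind, non-serious, later onset | Stopped | Prompt review, as an ordinary AE |
| Grade 4 symptom that is also an SAE | Stopped | Immediate pause |

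The window is the infusion day plus 3 full days (9.10). Symptoms that start later go on the adverse event log, so on the natural reading the reactogenicity exemption does not reach them. Only the second line shows the mismatch.

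**Step 3: an illustrative size for the delay.**

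- VRC01 infusions planned (Protocol Table 3-1): 23 × 4 + 23 × 4 + 16 × 1 = 200.
- Longest VRC01 infusion phase: 40 months in total less 6 months of follow-up after the last infusion = 34 months. At 30.44 days a month, 34 × 30.44 = 1035 days.
- Average rate if infusions are evenly spaced (an assumption): 200 / 1035 = 0.193 per day.
- Weekly review against a 72-hour review, worst case against worst case: 7 − 3 = 4 days; 4 × 0.193 = 0.77 infusions.
- If the 72 hours span a weekend (5 calendar days): 7 − 5 = 2 days; 2 × 0.193 = 0.39 infusions.

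Reporting lag from site to PSRT is taken as equal on both routes (an assumption). Because 34 months is an upper limit, the rate is a lower one: an infusion phase half as long would double the counts, to about 1.5 and 0.8. These infusions would not necessarily be prevented, since a prompt review does not itself hold dosing.

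**Step 4: likely frequency.** The documents give no rate for Grade 4 subjective symptoms. In HVTN 104 (4.7.1.3) most symptoms were mild and all 12 AEs considered product-related were mild, although malaise/fatigue, myalgia and headache, all exempted here, were the commonest. In VRC 606 (4.7.2) all six related AEs were Grade 1.

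**The case against.** **The two rules have different purposes.** Section 11.3 itself refers the reader to 7.3 for individual departures from the schedule. Stopping one person protects that person; Table 11-1 asks whether the product should be reviewed for everyone. The lists need not match. This stands, and it rules out a reading that some will be tempted by: that 7.3.3 and Table 11-1 contradict each other. Both can be followed as written.

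**The ranking of events looks inverted, but need not be.** A reader might infer incoherence from the fact that a related Grade 3 fever or vomiting, which does not stop the participant, gets prompt review while a Grade 4 headache does not. Temperature is measured and vomiting can be observed, so giving such signs prompt review is defensible. The point rests on the missing Grade 4 limit alone.

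**Other safeguards are substantial.** Safety forms are due the next business day (11.2.1). Sites are expected to tell the clinical safety specialist or regional medical liaison, both PSRT members, of serious concerns, and to phone the clinical safety line for urgent ones (11.2.2). Participants are contacted daily in the window, and a reaction worse than mild is in general seen by a clinician within 48 hours unless it is improving or resolved (9.10). The PSRT may suspend infusions at its discretion. It would therefore be wrong to infer that a Grade 4 reaction could escape oversight. But none of these routes sets a deadline for PSRT action or an automatic pause, and the daily HVTN Core review in 11.4.1 is specified for expedited-reporting, pause and prompt-review events.

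**A Grade 4 event may usually be serious.** If it is, the immediate pause applies. How often it is not depends on the DAIDS grading table and expedited reporting manual, which are not in the documents. The table nevertheless has a non-SAE row that includes Grade 4, so the protocol provides for such events.

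**The list may be deliberate.** The version history records a clarification about pruritus in this table, which suggests that the list was considered. It does not show that the Grade 4 scope was.

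**Conclusion.** The point holds as a minor gap in escalation. It covers only related, non-serious Grade 4 symptoms on the footnote b list with onset in the reactogenicity window. Related Grade 4 SAEs and later-onset related AEs are unaffected, as are the endpoints, the safety tabulations and every analysis in the SAP.

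The worst-case cost is a review about 2 to 4 days later. The 0.4 to 0.8 VRC01 infusions in that time assume even dosing over the longest possible infusion phase and are conditional on an event that should be rare and has no documented rate. The conclusion about the rules is firm, since it rests on the text alone. How often the gap would matter in practice cannot be settled from the documents.

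**What to change.** Limit the footnote b exemption to Grade 3, for example by stating that it does not apply at Grade 4. Related, non-serious Grade 4 subjective symptoms then enter the existing row: immediate email and forms from the site, prompt PSRT review, and the 72-hour limit. Whether to pause stays with the PSRT, and the Grade 3 exemption is unchanged.

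The change is a few words and uses the existing PSRT and HVTN Core process. The downside is a rare extra prompt review. If that review is not finished in 72 hours, the automatic pause could push an infusion past its visit window; under 7.3.2 it could not then be given, which would cost some PK data.

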11.4 Review of cumulative safety data

Routine safety review occurs at the start of enrollment and then throughout the study.

Reviews proceed from a standardized set of protocol-specific safety data reports. These reports are produced by the SDMC and include queries to the HVTN CRSs. Events are tracked by internal reports until resolution.

11.4.1 Daily review

Daily safety reviews are routinely conducted by HVTN Core for events requiring expedited reporting to DAIDS, and events that meet safety pause criteria or prompt HVTN 116 PSRT AE review criteria.

11.4.2 Weekly review

During the infusion phase of the trial, the HVTN 116 PSRT reviews clinical safety reports on a weekly basis and conducts calls to review the data as appropriate. After the infusions and the following two-week safety visit are completed, less frequent reporting and safety reviews may be conducted at the discretion of the HVTN 116 PSRT. HVTN Core reviews reports of clinical and laboratory AEs. Events identified during the review that are considered questionable, inconsistent, or unexplained are referred to the HVTN CRS clinic coordinator for verification.

11.5 Study termination

This study may be terminated early by the determination of the HVTN 116 PSRT, HVTN SMB, FDA, SAHPRA, NIH, Office for Human Research Protections (OHRP), or product developer. In addition, the conduct of this study at an individual HVTN CRS may be terminated by the determination of the IRB/EC and any applicable RE.

12 Protocol conduct

This protocol and all actions and activities connected with it will be conducted in compliance with the principles of GCP (ICHe6), and according to DAIDS and HVTN policies and procedures as specified in the *HVTN Manual of Operations*, DAIDS Clinical Research Policies and Standard Procedures Documents including procedures for the following:

- Protocol registration, activation, and implementation;
- Informed consent, screening, and enrollment;
- Study participant reimbursement;
- Clinical and safety assessments;
- Safety monitoring and reporting;
- Data collection, documentation, transfer, and storage;
- Participant confidentiality;
- Study follow-up and close-out;
- Quality control;
- Protocol monitoring and compliance;
- Advocacy and assistance to participants regarding negative social impacts associated with the clinical trial;
- Risk reduction counseling;
- Specimen collection, processing, and analysis;
- Ancillary studies, and
- Destruction of specimens.

Any policies or procedures that vary from DAIDS and HVTN standards or require additional instructions (eg, instructions for randomization specific to this study) will be described in the HVTN 116 *Study Specific Procedures*.

12.1 Social impacts

Participants in this study risk experiencing discrimination or other personal problems, resulting from the study participation itself. The HVTN CRS is obliged to provide advocacy for and assistance to participants regarding these negative social impacts associated with the clinical trial. If HVTN CRS staff have questions regarding ways to assist a participant dealing with a social impact, a designated NIAID or HVTN Core representative can be contacted.

Social harms are tabulated by the SDMC and are subjected to descriptive analysis. The goal is to reduce their incidence and enhance the ability of study staff to mitigate them when possible.

Summary tables of social impact events will be generated weekly, and made available for review by the protocol chairs, protocol team leader, and the designated NIAID representative.

12.2 Emergency communication with study participants

As in all clinical research, this study may generate a need to reach participants quickly to avoid imminent harm, or to report study findings that may otherwise concern their health or welfare.

When such communication is needed, the CRS will request that its IRB/EC and any applicable RE expedite review of the message. If this review cannot be completed in a timeframe consistent with the urgency of the required communication, the site should contact the participant first, and then notify the IRB/EC and any applicable RE of the matter as soon as possible.

13 Version history

The Protocol Team may modify the original version of the protocol. Modifications are made to HVTN protocols via clarification memos, letters of amendment, or full protocol amendments.

The version history of, and modifications to, Protocol HVTN 116 are described below.

Protocol history and modifications

Date: August 3, 2018

Protocol version: Version 2.0

Protocol modification: Full Protocol Amendment 1

- Item 1 Added in Appendices A, B, and E: Broad regulatory agency access to participant study records
- Item 2 Updated in Section 11.5, Section 15, and Appendices A, B, E: MCC changed to SAHPRA
- Item 3 Added in Section 8.4, Administration, in-line filter language
- Item 4 Clarified in Section 9.3: conditions upon when a participant may be replaced after enrollment
- Item 5 Clarified in Section 9.6 and Appendices H and I: vaginal biopsies can still be collected at late visits if the total number of biopsies has not been reached
- Item 6 Updated based on revisions made in Letter of Amendment 2 to Version 1.0 (US sites), dated September 18, 2017 and Amendment to Version 1.1 (RSA site), dated October 5, 2017
- Item 7 Updated based on revisions made in Letter of Amendment 1 (US sites) and Clarification Memo 3 (RSA site) to Version 1.0, dated March 24, 2017
- Item 8 Updated based on revisions made in Clarification Memo 2 to Version 1.0, dated December 16, 2016
- Item 9 Updated based on revisions made in Clarification Memo 1 to Version 1.0, dated June 17, 2016
- Item 10 Per live template changes on May 22, 2018, HIV infection moved from Section 7.3.6, Participant termination from the study, to Section 7.3.3, Discontinuing study product administrations for a participant, and other sections updated

Date: September 18, 2017

Protocol version: Version 1.0

Protocol modification: Letter of Amendment 2 / Same changes made in Version 1.1, dated October 5, 2017 for South African sites

- Item 1 Revised in Section 3, *Overview*; Section 5, *Objectives and endpoints*; Section 6, *Statistical considerations*; Appendices A and B, *Sample informed consent forms*: enrollment/sample sizes in Groups 3 and 5
- Item 2 References to the DAIDS table for grading of adverse events updated to current version 2.1 and clarifications to the protocol to be consistent with new version of the grading table
- Item 3 Clarified in Appendices L and M, *Procedures at HVTN CRS*: duration of screening period in footnote “a”
- Item 4 Updated in Section 8, *Study product preparation and administration*: revisions regarding VRC01 and VRC01LS based on the updated IBs

Date: March 24, 2017

Protocol version: Version 1.0

Protocol modification: Letter of Amendment 1 / Clarification Memo 3 (same content)

- Item 1 Clarified in Section 6.3, *Blinding*: lab staff will likely not be blinded to group assignment
- Item 2 Clarified in Section 7.3.1 *Delaying infusions for a participant*, Section 7.3.3 *Discontinuing study product administrations for a participant*, and Section 7.3.4 *Delaying biopsy collections for a participant*: details regarding participation in the study in the event of a pregnancy
- Item 3 Updated in Section 8.2, *Study product formulation*: VRC01 and VRC01LS descriptions
- Item 4 Revised in Section 8.3, *Preparation of study products*: IV infusion preparation instructions and holding times for study products after preparation
- Item 5 Added the requirement for an in-line filter to be in place for all IV administrations in Section 8.4, *Administration*
- Item 6 Updated in Section 8.4, *Administration*: Minimum infusion time period
- Item 7 Clarified in Section 10.3.2, *Immunohistochemistry*: biopsy collection instructions
- Item 8 Clarified in Section 11.3, *Safety pause and prompt PSRT AE review*, Table 11-1: pruritus is a subjective reactogenicity symptom
- Item 9 Clarified in Appendix M, *Procedures at HVTN CRS for Group 3, Visit 19* Colorectal biopsy collection

Date: December 16, 2016

Protocol version: Version 1.0

Protocol modification: Clarification Memo 2

- Item 1 Clarification in Section 9.3, *Enrollment visits*, Section 9.5, *Follow-up visits*, Appendices H-K, *Laboratory procedures*, and Appendices L-O,

Procedures at HVTN CRS: blood hormone levels will be assessed in persons born female only

Date: June 17, 2016

Protocol version: Version 1.0

Protocol modification: Clarification Memo 1

- Item 1 Deleted in Section 7.3.3, *Discontinuing study product administrations for a participant*: incorrect instruction for discontinuing infusions
- Item 2 Clarified Section 9.6, *Mucosal sampling*: procedures for cervicovaginal secretion collections and pregnancy testing
- Item 3 Corrected blood draw volumes in Appendices J & K: Laboratory procedures for Groups 4 and 5

Date: April 22, 2016

Protocol version: 1.0

Protocol modification: Original protocol

14 Document references (other than literature citations)

Other documents referred to in this protocol, and containing information relevant to the conduct of this study, include:

- Assessment of Understanding. Accessible through the HVTN protocol-specific website.
- Current CDC Guidelines. Revised Recommendations for HIV Testing of Adults, Adolescents, and Pregnant Women in Health-Care Settings. Available at <http://www.cdc.gov/mmwr/PDF/rr/rr5514.pdf>.
- Division of AIDS (DAIDS) Clinical Research Policies and Standard Procedures Documents. Available at <https://www.niaid.nih.gov/research/daids-clinical-research-policies-standard-procedures>
- Division of AIDS Protocol Registration Manual. Available at <https://www.niaid.nih.gov/sites/default/files/prmanual.pdf>
- Division of AIDS Table for Grading the Severity of Adult and Pediatric Adverse Events. Corrected Version 2.1, July 2017. Available at <http://rsc.tech-res.com/clinical-research-sites/safety-reporting/daids-grading-tables>
- The Manual for Expedited Reporting of Adverse Events to DAIDS. Version 2.0, January 2010. Available at <http://rsc.tech-res.com/clinical-research-sites/safety-reporting/manual>
- HVTN Certificate of Confidentiality. Accessible through the HVTN website.
- HVTN 116 Special Instructions. Accessible through the HVTN protocol-specific website.
- HVTN 116 Study Specific Procedures. Accessible through the HVTN protocol-specific website.
- HVTN Laboratory Manual of Operations. Accessible through the HVTN website.
- HVTN Manual of Operations. Accessible through the HVTN website.
- Dangerous Goods Regulations (updated annually), International Air Transport Association. Available for purchase at <http://www.iata.org/publications/dgr/Pages/index.aspx>
- Lab assay algorithm

- HVTN algorithm for diagnosis of HIV infections. Part of the HVTN Laboratory Manual of Operations (see above).
- International Conference on Harmonisation (ICH) E6 (R1), Guideline for Good Clinical Practice: Section 4.8, Informed consent of trial subjects. Available at <http://www.ich.org/products/guidelines/efficacy/article/efficacy-guidelines.html>
- Participants' Bill of Rights and Responsibilities. Accessible through the HVTN website.
- NIH *Guidelines for Research Involving Recombinant or Synthetic Nucleic Acid Molecules*. Available at <http://osp.od.nih.gov/biotechnology/biosafety/nih-guidelines>.
- NIH Policy on Reporting Race and Ethnicity Data: Subjects in Clinical Research. Available at <http://grants1.nih.gov/grants/guide/notice-files/NOT-OD-01-053.html>.
- Pharmacy Guidelines and Instructions for DAIDS Clinical Trials Networks, July 2008.
- Requirements for Source Documentation in DAIDS Funded and/or Sponsored Clinical Trials. Available at <https://www.niaid.nih.gov/sites/default/files/daids-sourcedocpolicy.pdf>
- Title 21, Code of Federal Regulations, Part 50. Available at <http://www.accessdata.fda.gov/scripts/cdrh/cfdocs/cfcr/CFRSearch.cfm?CFRPart=50>
- Title 45, Code of Federal Regulations, Part 46. Available at <http://www.hhs.gov/ohrp/humansubjects/guidance/45cfr46.html>

See Section 16 for literature cited in the background and statistics sections of this protocol.

15 Acronyms and abbreviations

Ab	antibody
Ad	adenovirus
AE	adverse event
ALP	alkaline phosphatase
ALT	alanine aminotransferase
ART	antiretroviral therapy
AST	aspartate aminotransferase
β-HCG	beta human chorionic gonadotropin
BMI	body mass index
bNAb	broadly neutralizing antibody
CAB	Community Advisory Board
CBC	complete blood count
CDC	US Centers for Disease Control and Prevention
CFR	Code of Federal Regulations
CI	confidence interval
CRF	case report form
CRPMC	NIAID Clinical Research Products Management Center
CRS*	clinical research site
CTL	cytotoxic T lymphocyte
DAERS	DAIDS Adverse Experience Reporting System
DAIDS	Division of AIDS (US NIH)
DHHS	US Department of Health and Human Services
EAE	adverse events requiring expedited reporting to DAIDS
EC	Ethics Committee
EIA	enzyme immunoassay
ELISA	enzyme-linked immunosorbent assay
FDA	US Food and Drug Administration
FHCRC	Fred Hutchinson Cancer Research Center
GCP	Good Clinical Practice
GLP	Good Laboratory Practice
GMP	Good Manufacturing Practice
HCV	hepatitis C virus
HLA	human leukocyte antigen
HVTN	HIV Vaccine Trials Network
IB	Investigator's Brochure
IBC	Institutional Biosafety Committee
